5.1 Study treatment

5.1.1 Investigational and control drugs

Novartis will supply the following study treatments in packaging of identical appearance:

- Secukinumab 150 mg provided in 1.0 mL in a prefilled syringe (PFS) for s.c. injection.
- Secukinumab placebo provided in 1.0 mL a PFS for s.c. injection (for matching 150 mg dose to blind 300 mg dosing)

NOTE: The PFS are packed in an open-label fashion from baseline through the Week 12 visit. Beginning Week 16, the PFS are packed in a double-blinded fashion for the remainder of the study.

5.1.2 Additional treatment

No additional treatment beyond investigational drug and control drug are included in this trial.

5.2 Treatment arms

Treatment Period 1

Once screening has been completed and patients have met the eligibility criteria, all patients will undergo 16 weeks of open-label treatment with secukinumab 150 mg s.c. self-administered at the site at baseline, Weeks 1, 2, 3, 4, 8, and 12.

All assessments at the scheduled visit will be performed before the patients receive the injection with the appropriate study medication for that visit.

At Week 12 and Week 16, all patients will be assessed for achieving the ASDAS inactive disease (<1.3) status, as well as for an inadequate response or a non-response. Patients will then be divided into three groups:

1. **Responders:** Patients achieving ASDAS inactive disease (total score < 1.3) status at Week 12 and Week 16 and who do achieve a decrease (improvement) from baseline in total ASDAS score at both Week 12 and Week 16.
2. **Inadequate responders:** Patients who have active disease, defined as an ASDAS total score of ≥ 1.3 at either Week 12 or Week 16, and who do achieve a decrease (improvement) from baseline in total ASDAS score at both Week 12 and Week 16.
3. **Non-responders:** Patients who exhibit no change or an increase (worsening) from baseline in total ASDAS score at either Week 12 or Week 16

Treatment Period 2 (Responders and Non-responders)

Responders: Patients achieving responder status will enter Treatment Period 2 and continue to receive 150 mg s.c. (one s.c. injection of secukinumab 150 mg) at Weeks 16, 20, 24, 28, 32, 36, 40, 44, and 48, as well as one matched placebo dose (s.c. injection) to maintain the integrity of the blind for the randomized Inadequate Responder group. This Responder group will be evaluated for maintenance of ASDAS inactive disease while remaining on 150 mg of secukinumab. All assessments at the scheduled visit will be performed before the patients receive the injection with the appropriate study medication for that visit.

NOTE: To minimize patient burden, at the Week 16 visit, the hs-CRP measurement that is part of the ASDAS calculation will be imputed from the Week 12 hs-CRP results to allow for assignment into the groups above. Historically, hs-CRP levels have varied little between Week 12 and Week 16 in previous studies of secukinumab in active AS.

Non-responders: Nonresponders will terminate the study at Week 16.

Treatment Period 2 (Inadequate Responders)

Inadequate responders will be randomized via the Interactive Response Technology (IRT) system in a 1:1 ratio to receive either secukinumab 300 mg (two s.c. injections of the 150 mg dose) or secukinumab 150 mg (one s.c. injection of the 150 mg dose and one s.c. injection of placebo) at Weeks 16, 20, 24, 28, 32, 36, 40, 44, and 48.

Patients will self-administer all secukinumab doses up to Week 48 after they have received training by the site to self-administer their secukinumab dose. While patients are encouraged to self-inject, continued assistance by the site or home nurse is acceptable. All assessments at the scheduled visit will be performed before the patients receive the injection with the appropriate study medication for that visit.

5.3 Treatment assignment and randomization

At Baseline through Week 12, the Interactive Response Technology (IRT) system will be used at each visit to dispense open-label treatment to enrolled patients. The system will specify unique medication numbers that will correspond to open-label treatment to be dispensed.

Responders: At Week 16 through Week 48, the IRT system will be used at each visit to dispense treatment and matching placebo to ASDAS-inactive disease responders. The system will specify unique medication numbers that will correspond to treatment to be dispensed.

Inadequate Responders: At Week 16, all ASDAS-inactive disease inadequate responder eligible patients will be randomized via IRT to one of the treatment groups in a ratio of 1:1 (secukinumab 300 mg or secukinumab 150 mg). The IRT system will assign a randomization number to the subject, which will be used to link the subject to a treatment group in the system and will specify unique medication numbers for treatment to be dispensed to the subject. The randomization number will not be communicated to any of the site staff. The IRT system will be used at each visit from Week 16 through Week 48 to dispense treatment.

The randomization numbers will be generated using the following procedure to ensure that treatment assignment is unbiased and concealed from patients and investigator staff. A subject randomization list will be produced by the IRT system provider using a validated system that automates the random assignment of subject numbers to randomization numbers. These randomization numbers are linked to the different treatment, which in turn are linked to medication numbers. A separate medication list will be produced by or under the responsibility of Novartis Drug Supply Management using a validated system that automates the random assignment of medication numbers to packs containing the investigational drug(s).

Randomization will be stratified by TNF-alpha inhibitor status (naive, inadequate responder). The stratification ensures balanced allocation of patients to treatment groups within the TNF-alpha inhibitor status strata.

The randomization scheme for patients will be reviewed and approved by a member of the Novartis Biometrics group.

5.4 Treatment Blinding

Patients, investigators/site staff, persons performing assessments, and Novartis study personnel will remain blinded to individual treatment assignment from the time of randomization (Week 16) for the inadequate responder group and responder group until the final database lock using the following methods:

1. Randomization data will be kept strictly confidential until the time of unblinding, and will not be accessible by anyone else involved in the study with the following exceptions:

- Specific vendors whose role in trial conduct requires their unblinding (e.g., IRT system)
 - Drug Supply Management (DSM);
2. The identity of secukinumab and placebo prefilled syringes (PFS) will be concealed by identical packaging, labeling, schedule of administration, and appearance.

There will be a database lock after all patients have completed the Week 52 visit and data are clean and complete.

Unblinding will only occur in the case of subject emergencies (see [Section 5.5.9](#)) and at the conclusion of the study.

5.5 Treating the patient

5.5.1 Patient numbering

Each subject is uniquely identified in the study by a combination of his/her four digit center number and three digit subject number. The center number is assigned by Novartis to the investigative site. After the subject has signed the ICF, the investigator or his/her staff will contact the IRT system and provide the requested identifying information for the subject to register them into the IRT system. The site must select the CRF book with a matching Patient Number from the EDC system to enter data. At each site, the subjects are numbered sequentially. (e.g. the first subject is assigned subject number 001, and subsequent patients are assigned consecutive numbers; the second subject is assigned subject number 002; the third subject is assigned subject number 003). Once assigned to a subject, a subject number will not be reused. If the subject fails to be randomized for any reason, the IRT system must be notified within 2 days and the reason for not being randomized will be entered on the Screening Phase Disposition Form within the eCRF. The appropriate eCRF(s) pages should also be completed.

5.5.2 Dispensing the study drug

All doses of study treatment will be self-administered by patients at the study site (or at home) after they have received training by the site on how to self-administer.

The study treatment packaging has a 2-part label. A unique medication number is printed on each part of this label, which corresponds to placebo or active treatment. Investigator staff will identify the study treatment packages to dispense to the subject by contacting the IRT and obtaining the medication numbers. Immediately before dispensing the package to the subject, detach the outer part of the label from the packaging and affix it to the source document (Drug Label Form) for that subject's unique subject number.

5.5.3 Handling of study and additional treatment

5.5.3.1 Handling of study treatment

Study treatment must be received by a designated person at the study site, handled and stored safely and properly, and kept in a secured location to which only the investigator and designees have access. Upon receipt, all study treatment should be stored according to the instructions

specified on the labels. Clinical supplies are to be dispensed only in accordance with the protocol.

Medication labels will be in English and comply with legal requirements in the U.S. They will include storage conditions for the study treatment but no information about the patient except for the medication number.

The PFS (150 mg active/placebo) sealed in their outer box must be stored in a locked refrigerator between 2°C and 8°C (36°F and 46°F) and protected from light. They must be carefully controlled in accordance with regulations governing investigational medicinal products and local regulations.

The Investigator must maintain an accurate record of the shipment and dispensing of study treatment in a drug accountability log. Monitoring of drug accountability will be performed by monitors during site visits or remotely and at the completion of the trial.

At the conclusion of the study, and as appropriate during the course of the study, the Investigator will return all unused study treatment, packaging, drug labels, and a copy of the completed drug accountability log to the Novartis monitor or to the Novartis address provided in the Investigator folder at each site.

Destruction of the unused drug should be done according to local requirements and after approval by Novartis clinical team.

5.5.3.2 Handling of additional treatment

5.5.4 Instructions for prescribing and taking study treatment

All study treatment will be self-administered subcutaneously after visit study assessments have been completed. Qualified staff will administer the injection only to those patients who are not able to self-administer the PFS injection. Detailed instructions on the self-administration of the study treatment will be described in the Instructions For Use (IFU) and provided to each subject.

The first study treatment administration will occur at the Baseline Visit **after** inclusion/exclusion criteria have been confirmed, all study scheduled assessments have been performed, and the scheduled blood samples have been drawn.

The patient will be instructed by the site staff, utilizing the IFU, on how to self-inject via PFS. Patients will be asked to raise any questions, if they have any, and then to proceed with self-injection. Self-injection will take place under the supervision of a site staff member. At the Week 1 and subsequent visits, patients will be asked to refer to the IFU and to proceed with self-injection of the study drug. While patients are encouraged to self-inject, continued assistance by the site or home nurse is acceptable.

Study treatment will be administered weekly following the baseline dose (Weeks 1, 2, 3, and 4) and every 4 weeks thereafter (at Week 8 until Week 48).

All dates and times of injections self-administered by the subject during the study must be recorded on the Dosage Administration Record eCRF. Immediately before dispensing the drug package to the subject, detach the outer part of the label from the packaging and affix it to the source document (Drug Label Form) for that subject's unique subject number.

The Investigator should promote compliance by instructing the subject to attend the study visits as scheduled and by stating that compliance is necessary for the subject's safety and the validity of the study. The subject should be instructed to contact the Investigator if he/she is unable for any reason to attend a study visit as scheduled or if he/she is unable for any reason to take the study treatment as prescribed. For patients unable to travel to the clinic for their study visit, flexible study visits (home nursing study visits) and telemedicine/telephone visits with direct to patient shipment of study drug are alternative options for all post-Baseline study visits. For more information regarding flexible study visits, please refer to the Site Manual for Home Visits (Flexible Study Visits).

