Investigational treatment	All investigational drug(s) whose properties are being tested in the study as well as their associated treatment controls. This includes any placebos, any active controls, as well as approved drugs used outside of their indication/approved dosage or tested in a fixed combination. Investigational treatment generally does not include protocol-specified concomitant background therapies when these are standard treatments in that indication
Medication number	A unique identifier on the label of each investigational/study drug package in studies that dispense medication using an IRT system
Protocol	A written account of all the procedures to be followed in a trial, which describes all the administrative, documentation, analytical and clinical processes used in the trial.
Premature subject withdrawal	Point/time when the patient exits from the study prior to the planned completion of all study treatment administration and/or assessments; at this time all study treatment administration is discontinued and no further assessments are planned, unless the patient will be followed for progression and/or survival
Randomization number	A unique identifier assigned to each randomized patient, corresponding to a specific treatment arm assignment
Study drug/ treatment	Any single drug or combination of drugs administered to the patient as part of the required study procedures; includes investigational drug (s), active drug run-ins or background therapy
Study/investigational treatment discontinuation	Point/time when patient permanently stops taking study/investigational treatment for any reason; may or may not also be the point/time of premature patient withdrawal
Subject Number	A number assigned to each patient who enrolls into the study
Variable	A measured value or assessed response that is determined in specific assessments and used in data analysis to evaluate the drug being tested in the study

Amendment 04

Amendment rationale

This protocol has been modified to add telemedicine/telephone study visits with direct to patient shipment of study drug as options available to participants unable to travel to the clinic for a study visit as the result of the COVID19 pandemic. Given the study design, which already allows flexible (home nursing) visits, the addition of telemedicine/telephone study visits with direct to patient shipment of study drug is believed to pose minimal risk to patient safety and data integrity.

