28. History of ongoing, chronic or recurrent infectious disease or evidence of tuberculosis infection as defined by either a positive purified protein derivative (PPD) skin test (the size of induration will be measured after 48-72 hours, and a positive result is defined as an induration of ≥ 5 mm or according to local practice/guidelines) or a positive central laboratory TB blood screening test as indicated in the assessment schedule in Table 6-1. Patients with a positive test may participate in the study if further work up (according to local practice/guidelines) establishes conclusively that the patient has no evidence of active tuberculosis. If presence of latent tuberculosis is established, then treatment according to local country guidelines must have been initiated
29. Pregnant or nursing (lactating) women where pregnancy is defined as the state of a female after conception and until the termination of gestation, confirmed by a positive human chorionic gonadotropin (hCG) laboratory test
30. Women of child-bearing potential, defined as all women physiologically capable of becoming pregnant, are excluded from the study unless they are using highly effective methods of contraception during dosing and for 16 weeks after stopping of study medication. All women of child-bearing potential must have a negative serum pregnancy test at Screening Visit 2, regardless of the method of contraception being used. Highly effective contraception methods include:
 - Total abstinence (when this is in line with the preferred and usual lifestyle of the subject). Periodic abstinence (e.g., calendar, ovulation, symptothermal, post-ovulation methods) and withdrawal are not acceptable methods of contraception
 - Female sterilization (have had surgical bilateral oophorectomy with or without hysterectomy) total hysterectomy or tubal ligation at least six weeks before taking study

drug. In case of oophorectomy alone, only when the reproductive status of the woman has been confirmed by follow up hormone level assessment

- Male sterilization (at least 6 months prior to screening). For female subjects on the study, the vasectomized male partner should be the sole partner for that subject
- Barrier methods of contraception: Condom or Occlusive cap (diaphragm or cervical/vault caps).

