General Medical history / previous therapies	X																						See section 6.3
Relevant AS medical history / current medical conditions	X																						See section 6.3
Washout evaluation / instruction	S																						See Table 5-1
Modified NY criteria	S	S	S																				See section 13.2
Radiologic evidence (x-ray) to central reader		X																					See section 6.6.9

Period	SCR ¹		Treatment Period 1 (Open-Label)								Treatment Period 2 (Double-Blind or Open-Label)								Telemedicine/ telephone visit	Unscheduled	Notes		
	Week	-13 to -3	-2 to BL	BL	1	2	3	4	8	12	16	20	24	28	32	36	40	44				48	52/Study Completion/ EOS ²
Visit No	1	2	3	4	5	6	7	8	9	10	11	12	13	14	15	16	17	18	19				
Assessments																							
Smoking and alcohol history			X																				See section 6.3
Cardiovascular medical history	X																						See section 6.3
Physical Exam ³		S	S				S	S	S	S	S	S	S	S	S	S	S	S	S				See section 6.6.4
Weight		X	X							X													See section 6.6.6
Height		X																					See section 6.6.6
Vital signs		X	X	X	X	X	X	X	X	X	X	X	X	X	X	X	X	X	X	X		X	See section 6.6.5
Chest X-ray		X																					See section 6.6.2
ECG		X																					See section 6.6.3
Prior/ Concomitant medication/ non-drug therapy	X	X	X	X	X	X	X	X	X	X	X	X	X	X	X	X	X	X	X	X	X	X	See section 5.5.7

Period	SCR ¹		Treatment Period 1 (Open-Label)								Treatment Period 2 (Double-Blind or Open-Label)												
Week	-13 to -3	-2 to BL	BL	1	2	3	4	8	12	16	20	24	28	32	36	40	44	48	52/Study Completion/ EOS ²	Telemedicine/ telephone visit	Unscheduled	Notes	
Visit No	1	2	3	4	5	6	7	8	9	10	11	12	13	14	15	16	17	18	19				
Assessments																							
IRT transaction	S	S	S	S	S	S	S	S	S	S	S	S	S	S	S	S	S	S	S	S	X		See section 5.3
Administration of s.c. study treatment via PFS			X	X	X	X	X	X	X	X	X	X	X	X	X	X	X	X	X		X		See section 5.5.4
Adverse Events/SAEs (inc. injection site reaction & occurrence of infections)	X	X	X	X	X	X	X	X	X	X	X	X	X	X	X	X	X	X	X	X	X	X	See section 7.1 – 7.2
QuantiFERON TB-Gold test		X																					See section 6.6.1
Hematology, blood chemistry ⁴		X	X						X	X			X			X				X			See section 6.6.7.1 - 6.6.7.2
Serum pregnancy test		X																					See section 6.6.8
Urinalysis/Urine pregnancy test			X				X		X	X		X		X		X				X			See section 6.6.7.3 and 6.6.8
HLA-B27		X																					See section 6.6.7.4

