6.6.8 Pregnancy and assessments of fertility

Secukinumab must not be given to pregnant women; therefore effective methods of birth control must be used for women of child-bearing potential (see exclusion criteria definitions, [Section 4.2](#)).

A serum β -hCG test will be performed in all women of child bearing potential at Screening Visit 2; and a local urine pregnancy test at Visits 3, 7, 9, 10, 12, 14, 16 and 19. A positive urine pregnancy test requires immediate interruption of study treatment until serum β -hCG is performed and found to be negative. If positive, the subject must be discontinued from the trial.

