7.6 Pregnancy Reporting

All pre-menopausal women who are not surgically sterile will have a urine pregnancy test. A positive urine pregnancy test requires immediate interruption of study drug until serum β -hCG is performed and found to be negative.

To ensure patient safety, each pregnancy occurring while the patient is on study treatment must be reported to Novartis within 24 hours of learning of its occurrence. The pregnancy should be followed up to determine outcome, including spontaneous or voluntary termination, details of the birth, and the presence or absence of any birth defects, congenital abnormalities, or maternal and/or newborn complications.

Pregnancy should be recorded on the Pharmacovigilance Pregnancy Form and reported by the investigator to the local Novartis Drug Safety and Epidemiology Department. Pregnancy follow-up should be recorded on the same form and should include an assessment of the possible relationship to the study treatment.

Any SAE experienced during the pregnancy and unrelated to the pregnancy must be reported on a SAE form.

8 Data review and database management

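### For patients who cannot travel, Table 6-1 schedules the injection at a telephone visit but not the urine pregnancy test that Protocol 6.6.8 still requires, and no way of doing the test is given

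*Protocol*

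**What the plan says.** **Visit mode.** Protocol 5.5.4 and Section 6 offer two alternatives to patients who cannot travel to the clinic: a home-nursing visit, or a telemedicine or telephone visit (below, a telephone visit) with drug shipped to the patient. In both places "telemedicine/telephone visits with direct to patient shipment of study drug are alternative options for all post-Baseline study visits". Neither place says which alternative to use when a test is due.

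**Schedule.** Table 6-1 has a column for the telephone visit. The row "Administration of s.c. study treatment via PFS" is marked in it. The row "Urinalysis/Urine pregnancy test" is not.

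**Pregnancy testing.** Protocol 6.6.8 requires "a local urine pregnancy test at Visits 3, 7, 9, 10, 12, 14, 16 and 19", with no exception by mode of visit. It continues: "A positive urine pregnancy test requires immediate interruption of study treatment until serum" hCG has been done and is negative. Section 7.6 repeats the rule ("A positive urine pregnancy test requires immediate interruption of study drug until serum") and applies the urine test to all pre-menopausal women who are not surgically sterile.

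**Order of procedures.** 5.5.4 places self-injection after the visit's assessments. 6.6 places safety assessments before dosing and lists pregnancy assessment among them.

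**Rationale for telephone visits.** Amendment 04 judged the added risk to be minimal, on the reasoning "Given the study design, which already allows flexible (home nursing) visits".

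**The concern.** Drug can reach the patient by post and be injected at home, while the check that is meant to stop dosing in a pregnant woman is absent from the list of what a telephone visit contains. If the test is not done, the interruption rule in 6.6.8 and 7.6 cannot be triggered by it, and monthly dosing continues.

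The protocol requires contraception as well, yet it still schedules seven urine tests after Baseline. It therefore does not treat contraception alone as enough. The argument from home nursing in Amendment 04 does not settle the matter either: a nurse visit puts a professional in the home, whereas a telephone visit needs some other arrangement for the test, and none is described.

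**Working it through.** No figure in the plan addresses this point, so there is none to reproduce. The check has two parts.

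**1. Reading Table 6-1.** In the text read from the PDF, the injection, hematology and urine-test rows have 24 cells against 23 in the header, so one extra cell falls late in each row. Two alignments are possible.

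- *From the left:* the injection would be marked at Week 52 and at unscheduled visits but not at telephone visits, and the urine test would be missing at Visit 19. This contradicts the Week 48 last dose (5.6.1), the rule against dosing at unscheduled visits (Section 6), and the visit list in 6.6.8.
- *From the right:* the injection is blank at Week 52 and marked for the telephone visit. The urine test is marked at Visit 19 and blank for the telephone visit. The last hematology mark falls on Visit 19, as 6.6.7.1 says.

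Only the second fits the text, and it is the reading used here.

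**2. Time from the latest test to each dose.** Inputs, from 5.2, 6.6.8 and Table 6-1:

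- Doses after Baseline: Weeks 1, 2, 3, 4, 8, 12, 16, 20, 24, 28, 32, 36, 40, 44 and 48, which is 15 injections.
- Urine tests: Baseline, then Weeks 4, 12, 16, 24, 32, 40 and 52 (Visits 7, 9, 10, 12, 14, 16 and 19). The Week 52 test follows the last dose, so six post-Baseline visits carry both a test and an injection.

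Gap = dose week − week of the latest test on or before that dose. With the Week 16 test done, the gaps at Weeks 20, 24, 28, 32, 36, 40, 44 and 48 are:

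| Test missed at | Gaps (weeks) | Longest | Doses over 8 weeks |
|---|---|---|---|
| none (as planned) | 4, 0, 4, 0, 4, 0, 4, 8 | 8 | 0 of 8 |
| Visit 12 | 4, 8, 12, 0, 4, 0, 4, 8 | 12 | 1 |
| Visit 14 | 4, 0, 4, 8, 12, 0, 4, 8 | 12 | 1 |
| Visit 16 | 4, 0, 4, 0, 4, 8, 12, 16 | 16 | 2 |
| Visits 12 and 14 | 4, 8, 12, 16, 20, 0, 4, 8 | 20 | 3 |
| Visits 12 and 16 | 4, 8, 12, 0, 4, 8, 12, 16 | 16 | 3 |
| Visits 14 and 16 | 4, 0, 4, 8, 12, 16, 20, 24 | 24 | 4 |
| Visits 12, 14 and 16 | 4, 8, 12, 16, 20, 24, 28, 32 | 32 | 6 |

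If every post-Baseline visit is by telephone and no test is done, the latest test is always the Baseline one (Week 0). The longest gap is then 48 − 0 = 48 weeks, with all 15 injections after that test. This is the upper bound; 32 weeks is not, because it assumes a test at Week 16.

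The 8-week yardstick is only the longest gap in the planned schedule. The protocol sets no maximum interval from test to dose.

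**The case against.** **The test is still required.** This is the strongest point. 6.6.8 and 7.6 make no exception for telephone visits, and 5.5.4 and 6.6 put dosing after assessments. SAP Table 5-1 lists a missed pregnancy procedure as a deviation (O04). A reader might infer from the blank cell that the protocol permits a woman to keep injecting untested. The documents do not support that: injecting without a due test would depart from the text. What remains is a conflict between the schedule and the text. Sites work from the schedule, the schedule says what a telephone visit contains, and O04 records the miss without holding the dose.

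**Staff need not be present.** 6.6.8 asks for a local urine test and does not say who runs it. This stands. The obstacle is the lack of a kit and an instruction.

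**Other safeguards apply.** Women of child-bearing potential must be "using highly effective methods of contraception during dosing and for 16 weeks after stopping of study medication". Adverse events are collected at telephone visits, home-nursing and unscheduled visits are available, and pregnancy, however detected, requires discontinuation (5.6.2). These limit the risk but do not replace the scheduled test.

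**A manual may cover it.** The Site Manual for Home Visits was not available here. The protocol cites it for home-nursing visits, and it could hold a procedure for telephone visits too.

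**Blood samples.** The hematology and chemistry row is also blank for telephone visits, and a reader might extend the point to it. No passage makes dosing depend on a same-visit blood result, and the visible text does not say that home nurses draw blood, so the point is not extended.

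**The primary endpoint.** A reader might also infer harm here, since ASDAS needs CRP (6.5.1) and a missing component counts as nonresponse (SAP 2.5.3). The visible text does not show how CRP would be obtained at a telephone visit, so no such claim is made.

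**Conclusion.** The concern holds as a conflict between documents on a safety check. For patients unable to travel, the telemedicine column of Table 6-1 schedules the injection without the pregnancy test, while 6.6.8, 7.6, 5.5.4 and 6.6 together require the test before dosing. Nothing in the visible text says how to do the test by telephone.

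Per patient, the longest test-to-dose gap moves from 8 weeks to 12 or 16 for one missed test among Visits 12, 14 and 16, to 32 if all three are missed, and to 48 at the bound. The documents do not say how many patients would use telephone visits or how many are women of child-bearing potential, so the frequency is unknown.

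The conclusion rests on aligning Table 6-1 from the right and on no unseen manual already supplying the procedure. It is a cheap improvement worth making, with no bearing on sample size or analysis.

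**What to change.** In Table 6-1, mark the urine pregnancy test in the telemedicine column for women of child-bearing potential. The row also covers urinalysis, so the footnote should limit the mark to the pregnancy test. Repeat the footnote in 5.5.4 and 6.6.8:

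> When a visit at which a urine pregnancy test is due is done by telephone, a urine pregnancy kit is sent with the shipment and a negative result is confirmed with the site before injection (Visits 7, 9, 10, 12, 14 and 16; also tested at Visit 19). A positive result holds the dose under 6.6.8, and serum hCG is obtained at an in-person, home-nursing or unscheduled visit.

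If the Site Manual already contains this procedure, a cross-reference in the footnote is enough.

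Cost: one table mark, a short footnote, kits in the shipments for these patients, and one call before injection at the visits concerned. The test is already scheduled, so no assessment is added, and the SAP does not change.
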